7.8 EFFICACY ANALYSIS

The primary and secondary endpoints will be derived from the daily diary data entered by patients.

Two-sided tests at a significance level of $\alpha=5\%$ will be used throughout unless otherwise stated. The null hypothesis is that lubiprostone is equal to placebo against the alternative that lubiprostone is different to placebo. All analyses will be performed using the FAS. Analyses specified for the PP are to be regarded as supportive evidence. There will be no adjustment for multiplicity.

All efficacy endpoints will be summarized by treatment and visit. If baseline measures are also defined and collected for an efficacy endpoint then change from Baseline at each visit will also be presented by summary statistics by treatment and visit. Change from baseline will be calculated as (post-baseline value) – (baseline value). Baseline is defined as the last recorded measurement prior to treatment.

For diary data, baseline values will be the average of all diary data from the screening period (Days -14 through -1, inclusive, relative to day of first dose). If more than 14 days of diary data are collected during the screening period only the data from Day -14 onwards will be used. If fewer than 8 days are available then the baseline value will be set to missing.

Centers may be pooled geographically if necessary for analysis purposes. This will be determined before database lock.

CROSS-REGIONAL TEMPLATE

Template Number: C-TMPL-DO-801

Page: 17 of 28

Version Number: 1.2

Effective Date: 14 Sep 2015

This version replaces: 1.1

Parent Document: C-SOP-DO-800

Template Title: Statistical Analysis Plan (Legacy Takeda)

For weekly SBM frequency, at least 4 days of diary data are required to compute a weekly estimate, if there are less than 4 days recorded in a week then the SBM frequency for that week will be set to missing.

As the primary endpoint is within the first week of study treatment and only 4 days of diary collection are required it is not anticipated that missing values should be a cause of concern therefore the LOCF technique will be used to impute missing values for efficacy analysis purposes only. For a given subject, the most recent nonmissing data point will be carried forward to the subsequent week where data are missing. Details for each efficacy parameter are given below. It is expected, based on previous studies, that the number of subjects with in-sufficient post baseline data for the primary endpoint will be small therefore a simple approach to handling missing data will be used. Where there is no post baseline efficacy data then the baseline value will be used, it is expected that the number of SBMs should increase for those on treatment, therefore using a baseline value for missing post baseline data assumes no treatment effect, this approach can be considered conservative,. To examine the effect of the requirement to have at least a minimum of 4 days post baseline efficacy data for the primary endpoint an additional analysis, stratified by center, of the primary endpoint, using the stratified van Elteren test [2], will be conducted using all valid SBM data post baseline even when less than 4 days data is present, only where there is no post baseline data will baseline be used in this analysis.

An SBM is defined as any BM that does not occur within 24 hours after rescue medication use. Certain periods after taking rescue medication will be defined as “blackout periods” during which BMs are considered as non-spontaneous. Blackout periods, including those with missing or partial times for rescue medication use in the diary, will be handled as follows:

0-24 hours post rescue medication intake if the time is fully specified.

0-24 hours post rescue medication intake if the hour is present, but the minute is missing. The blackout time will commence from the imputed time. If the minutes are incomplete or missing from either the rescue medication or bowel movement entry then it is assumed that the missing values are zero and an imputed time will be calculated. e.g.

1	5			=	1	5	0	0
2	1	5		=	2	1	5	0

0-48 hours, beginning from midnight on the day the rescue medication intake is recorded for, if the hour is missing from the time entry for the rescue medication.

Box plots will be produced for each weekly measure (SBM frequency, mean degree of straining, mean degree of stool consistency and weekly abdominal symptoms scores) by treatment over time from baseline to Week 4. Additionally graphs presenting histograms of SBM frequency will also be produced by treatment for each week.

CROSS-REGIONAL TEMPLATE

Template Number:	C-TMPL-DO-801	Page:	18 of 28
Version Number:	1.2	Effective Date:	14 Sep 2015
This version replaces:	1.1		
Parent Document:	C-SOP-DO-800		
Template Title:	Statistical Analysis Plan (Legacy Takeda)		

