5.0 ANALYSIS ENDPOINTS

Primary Endpoint

Spontaneous bowel movement (SBM) frequency in Week 1 of study drug administration.

Secondary Endpoints

SBM frequency (Week 2, 3, and 4).

Proportion of subjects who have a SBM within 24 hours after first dose.

Mean degree of straining (Week 1, 2, 3, and 4).

Mean degree of stool consistency (Week 1, 2, 3, and 4).

Weekly abdominal symptoms score (bloating and discomfort) (Week 1, 2, 3, and 4).

Additional Endpoints

Quality of life evaluation using the standard Patient Assessment of Constipation—Quality of Life (PAC-QOL) Questionnaire.

Safety

The safety of lubiprostone will be evaluated by the following parameters:

Adverse events (AEs)

Clinical laboratory values.

Vital signs, including body temperature, blood pressure, heart rate, and body weight.

Physical examination.

Exploratory Endpoints

CCI

CROSS-REGIONAL TEMPLATE

Template Number: C-TMPL-DO-801 **Page:** 8 of 28
Version Number: 1.2 **Effective Date:** 14 Sep 2015
This version replaces: 1.1
Parent Document: C-SOP-DO-800
Template Title: Statistical Analysis Plan (Legacy Takeda)

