7.0 METHODS OF ANALYSIS AND PRESENTATION

7.1 GENERAL PRINCIPLES [OR CONSIDERATIONS]

Continuous data will be summarized using number of subjects (N), mean, standard deviation (SD), median, minimum, and maximum. Summary statistics for continuous data will only include subjects with a non-missing value for the data being summarized.

Categorical data will be summarized using the number and percent of subjects for each category where appropriate. Missing categories will be used for categorical data when missing data is present. The calculation of percentages will take into account missing responses.

All confidence intervals, statistical tests, and resulting p-values will be reported as 2-sided unless otherwise stated. P-values (when rounded to three decimals) less than or equal to α ($=0.05$) are reported as “statistically significant”.

Means, LS means, and medians will be presented to 1 more decimal place than the recorded data. Where presented, SDs and standard errors will be presented to 2 more decimal places than the recorded data. Confidence intervals for parameter estimates will be presented using the same number of decimal places as those recorded for the parameter point estimate.

Alternative methods of analysis of the data may be considered prior to un-blinding should some of the assumptions underlying the proposed analyses not be met. However, the reasons for any departures from the planned approach and methods will be documented fully.

Centers may be pooled geographically if necessary for analysis purposes.

Version 9.4 or later of SAS®, will be used to provide all data summaries, statistical analyses, and data listings.

CROSS-REGIONAL TEMPLATE

Template Number: C-TMPL-DO-801

Page: 10 of 28

Version Number: 1.2

Effective Date: 14 Sep 2015

This version replaces: 1.1

Parent Document: C-SOP-DO-800

Template Title: Statistical Analysis Plan (Legacy Takeda)

Study Visit Windows

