7.8.2 Secondary Efficacy Endpoint(s)

The interaction of treatment and center and the effect of dose reduction will not be examined for any secondary endpoints. All secondary endpoints will be analyzed for the FAS only.

SBM frequency at Week 2, 3 and 4

The secondary endpoint will be analyzed as specified for the primary endpoint separately for each week.

Additionally for patients with a missing Week 2 frequency estimate (where diary days < 4 in Week 2) the Week 1 estimate will be carried forward, if available. For the worse-case analysis all missing Week 2 values will be assigned the lowest SBM frequency for week 2.

Proportion of subjects with an SBM within 24 hours after first dose

The 24 hour period will be taken from the time of the first recorded dose in the patient diary. If the efficacy data is missing for the first 24 hours following this dose then it will be assumed that the patient did not experience any BM (including SBMs) during this period, this is based on the assumption that a patient is more likely to complete the diary on any particular day if they experience a BM than if they did not. The proportion of subjects with an SBM within 24 hours after first dose in Week 1 will be analyzed by a Cochran-Mantel-Haenszel (CMH) test stratified by center. Additionally a logistic regression model will be used with treatment and center as factors as a sensitivity analysis. The estimated odds ratio and associated 95% CI for both methods will be presented to aid interpretation of the clinical effect.

Mean Degree of Straining (Week 1, 2, 3, and 4)

For each BM patients should indicate the degree of straining associated with that BM. The degree of straining is a 5 point scale:

0 = No straining

1 = Mild straining

2 = Moderate straining

3 = Strong straining

4 = Very strong straining

CROSS-REGIONAL TEMPLATE

Template Number: C-TMPL-DO-801

Page: 20 of 28

Version Number: 1.2

Effective Date: 14 Sep 2015

This version replaces: 1.1

Parent Document: C-SOP-DO-800

Template Title: Statistical Analysis Plan (Legacy Takeda)

For each subject, the mean degree of straining will be averaged for all SBMs in a given week. The mean degree of straining will then be analyzed by van Elteren tests, stratified by center, at Weeks 1, 2, 3, and 4 separately. A related 95% confidence interval and point estimate will be provided for the treatment difference; the confidence interval will be estimated by inverting the hypothesis test.

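### Twenty unadjusted secondary tests would carry the same label of statistical significance as the primary test, even if the primary fails

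*SAP*

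**What the plan says.** - **Error rate.** SAP 7.8 opens its testing rules with "Two-sided tests at a significance level of" 5%, to be used throughout unless otherwise stated. It adds: "There will be no adjustment for multiplicity". Protocol 13.1.3 has the same rule.
- **Label.** SAP 7.1 begins "P-values (when rounded to three decimals) less than or equal to" 0.05 and says such p-values are reported as statistically significant. The rule is a general principle and names no endpoint.
- **Primary.** There is one primary endpoint, "Spontaneous bowel movement (SBM) frequency in Week 1 of study drug administration", with one primary analysis: the van Elteren test on the FAS (SAP 7.8.1).
- **Secondaries.** SAP 5.0 and 7.8.2 list SBM frequency at Weeks 2, 3 and 4, the endpoint "Proportion of subjects who have a SBM within 24 hours after first dose", and straining, stool consistency and abdominal symptoms at each of Weeks 1 to 4. For SBM frequency, "The secondary endpoint will be analyzed as specified for the primary endpoint separately for each week". Straining and consistency are also tested week by week. Bloating and discomfort are tested separately from each other and by week.
- **What is absent.** Neither document names a key secondary endpoint, sets a testing order, makes secondary testing depend on the primary, or calls secondary p-values nominal or descriptive. SAP 7.8 describes only the per-protocol analyses as supportive.

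**The concern.** Planning no adjustment is defensible when secondary results are read as descriptive. Applying one significance label to every p-value is harmless when only one test matters. The difficulty is the combination: the plan leaves 20 comparisons uncontrolled and instructs the report to describe each one that crosses 0.05 in the words used for the primary result.

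The secondaries have a job to do. Protocol 6.2 uses the later SBM weeks to back up a continuing effect, and the symptom endpoints to round out the evaluation of treatment. Protocol 4.2 and 6.2 say the study is designed to support registration. Followed literally, the plan would report a lone result such as bloating at Week 3 as statistically significant whether or not Week 1 SBM frequency succeeded, and nothing would tell the reader that it was one of 20 attempts.

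**Working it through.** **The plan's own figure.** The documents give no family-wise error rate. The only related figure is the sample size in SAP 6.0, for one two-sided test at 0.05 with 90% power, means 5.9 and 4, and SD 4. By the normal approximation, n per arm = 2 × [4 × (1.960 + 1.282) / 1.9]² = 93.1. Dividing by the Wilcoxon efficiency 3/π gives 97.5, so 98 per arm and 196 in total, against the stated 198. A t-based calculation gives 200. The plan's figure reproduces, and it confirms that the primary is planned as a single test at the full 0.05.

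**Count of secondary tests (SAP 5.0 and 7.8.2)**

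| Endpoint | Tests |
|---|---|
| SBM frequency, Weeks 2–4 | 3 |
| SBM within 24 hours | 1 |
| Straining, Weeks 1–4 | 4 |
| Stool consistency, Weeks 1–4 | 4 |
| Bloating, Weeks 1–4 | 4 |
| Discomfort, Weeks 1–4 | 4 |
| Total | 20 |

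PAC-QOL, the sensitivity models and the redacted exploratory endpoint are not counted.

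**If no secondary effect is real**

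- Expected number of false significant results: 20 × 0.05 = 1.0, whatever the correlation.
- Independent tests, either direction: 1 − 0.95²⁰ = 0.642. Rounding p to three decimals moves the cut-off to just under 0.0505, which gives 1 − 0.9495²⁰ = 0.645, a trivial change.
- Independent tests, false result favouring lubiprostone only: 1 − 0.975²⁰ = 0.397.

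**Allowing for correlation.** The tests are not independent. The same subjects are measured each week, LOCF copies values forward (SAP 7.8), and the symptoms are related. The documents give no correlations, so the values below are assumptions. The test statistics are taken as jointly normal.

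One common correlation among all 20 statistics:

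| Assumed correlation | At least one false result, either direction | At least one favouring lubiprostone |
|---|---|---|
| 0 | 0.64 | 0.40 |
| 0.3 | 0.54 | 0.28 |
| 0.5 | 0.42 | 0.21 |
| 0.7 | 0.29 | 0.145 |

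Separate correlations between weeks of one endpoint and between endpoints in one week (200,000 simulated draws, either direction):

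| Between weeks / between endpoints | At least one false result |
|---|---|
| 0.3 / 0.1 | 0.615 |
| 0.5 / 0.3 | 0.543 |
| 0.7 / 0.3 | 0.481 |
| 0.8 / 0.5 | 0.383 |
| 0.9 / 0.6 | 0.298 |

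Across the second table the chance is about 6 times (0.298 / 0.05) to 12 times (0.615 / 0.05) the nominal 5%.

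**The case against.** The case for leaving the plan alone has five parts.

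1. *The decision is disclosed and the main conclusion is safe.* Both documents state it, and there is one primary endpoint, one time point and one primary test. This stands. A reader might infer that the missing adjustment inflates the trial's primary error rate; it does not.
2. *A false secondary result is not shown to be likely.* A reader might infer from the 64% that at least one false claim is more probable than not. That figure is the independence ceiling. With weekly repeats and LOCF the chance can fall below one half, for example to 0.48 at 0.7 / 0.3 and 0.42 at a common 0.5. The documents give no correlations that would settle it. This stands, and the result must be given as a range.
3. *Only errors in lubiprostone's favour would help its case.* This is fair, and it lowers the figures to about 40% at most.
4. *The complete null is a worst case.* Protocol 4.1.4 reports an overall SBM effect across all weeks (p<0.0001) in both US studies, so real effects at Weeks 2 to 4 are plausible. The same section gives no results for straining, consistency, bloating or discomfort, so the reassurance does not reach those 16 tests.
5. *No misuse is announced.* The Protocol study summary lists no secondary objectives. Protocol 6.2 gives the secondaries a supporting role, and its registration wording describes the study as a whole. A reader might infer that isolated weekly results are intended as formal or label claims; neither document says so.

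What survives is the wording. If the secondaries are only supportive, the general label in SAP 7.1 says more than the plan can back.

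**Conclusion.** The point holds as a reporting and labelling defect. Under the plan as written, any of 20 ungated secondary tests that reaches 0.05 is called statistically significant on the same footing as the primary, including when the primary has failed.

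If no secondary effect is real, at least one such false label arises with probability at most about 64%, and roughly 30% to 60% under positive correlation. In lubiprostone's favour alone, the probability is about 40% if the tests are independent and about 15% to 28% at common correlations of 0.7 to 0.3. These sizes rest on the complete null and on assumed correlations. The count of 20, the lack of adjustment and the unrestricted label come directly from the documents. The primary inference is unaffected.

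**What to change.** Before unblinding:

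- **SAP 7.1:** limit the term statistically significant to the primary test.
- **SAP 7.8:** state that all secondary and additional p-values are nominal.

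If the sponsor wants confirmatory secondary claims, it should instead pre-specify a fixed sequence in SAP 7.8. Each step would be tested at two-sided 0.05, only after the primary succeeds, and testing would stop at the first non-significant result. All other secondary and additional p-values would be nominal, and the SAP 7.1 label would cover only the primary and the sequence. One possible order is SBM frequency at Week 2, Week 3 and Week 4, then SBM within 24 hours. The documents do not dictate an order, and the sponsor may prefer to include symptom endpoints, so the choice is the sponsor's.

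The cost is SAP wording. No alpha is taken from the primary, its power does not change, and no extra subjects are needed. The downside is that secondary results outside any such sequence, or after a failed step, cannot be called statistically significant.

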6.0 STUDY DESIGN AND DESCRIPTION

6.1 Study Design

This is a phase 3, randomized, double-blind, parallel-group, placebo-controlled study in subjects with CIC as determined by the Rome III Diagnostic Criteria for Functional Constipation [4].

This study consists of a 14-day Screening Period and a subsequent 4-week (28 days) Double-Blind Treatment Period in which subjects will receive either lubiprostone or matching placebo twice a day. Subjects will be randomized to either active lubiprostone or placebo in a 1:1 ratio.

During the Screening Period, the defecation behavior of each subject is recorded in a diary to confirm he/she has constipation. Use of all existing laxatives is stopped at the beginning of the Screening Period (Visit 1). Subjects are instructed not to change their diet or lifestyle habits during the study. A total of 10 mg of bisacodyl suppository (or any equivalent drug) may be prescribed as a standard rescue medication if a subject has no adequate bowel movement for 3 consecutive days during the Screening Period of the study. When bisacodyl suppository does not improve constipation, glycerin enema (or equivalent drug) will be given. Subjects are instructed to complete their diaries before using rescue medications.

The subject diary will be distributed on Study Days -15, -1, 8 and 15. Subjects will be instructed to keep the diary every day including on the morning of Visit 1.

If the rescue medications fail to improve constipation, the investigator may decide to use another rescue medication. The recommendation may include a medication from the excluded medication list other than any form of polyethylene glycol (PEG), linaclotide, methylnaltrexone, or prucalopride, all of which are considered prohibited rescue medications. No rescue medication may be given 24 hours prior to and until 48 hours after the first dose of the study drug (Day 1). Subjects who use a rescue medication within 24 hours before the first dose of study drug on Day 1 should be withdrawn from the study. Those who use a rescue medication within 48 hours after dosing on Day 1 will be discontinued from the study by the investigator. The dose and mode of administration of rescue medications must be recorded in the electronic case report form (eCRF).

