6.2 Justification for Study Design, Dose, and Endpoints

Constipation is generally considered as infrequent and difficult passage of stool. It is typically defined as a condition of having fewer than 3 BMs a week [\[1\]](#). However, stool shape and the subject's own perception other than stool frequency need to be considered for evaluation of disturbance in bowel movement [\[5\]](#).

The Rome Foundation, an international organization that classifies functional gastrointestinal disorders, published the definition of functional constipation in 2006 ("constipation without gastrointestinal tract abnormalities") as shown in [Table 6.a](#). The Rome Foundation requires use of multiple indices for diagnosis of functional constipation. The definition is characterized by the "criterion fulfilled for the last 3 months with symptom onset at least 6 months prior to diagnosis" [\[4\]](#).

Table 6.a Rome III Diagnostic Criteria for Functional Constipation

C3. Functional Constipation (*)

1. Satisfies at least 2 of the following:
 - a) Straining in at least 1 out of every 4 bowel movements.
 - b) Scybalum stool or hard feces in $\geq 25\%$ of defecations.
 - c) Sensation of incomplete evacuation in $\geq 25\%$ of defecations.
 - d) Sensation of anorectal obstruction/blockade in $\geq 25\%$ of defecations.
 - e) Manual maneuvers to facilitate defecation (eg, digital evacuation, support of the pelvic floor) in $\geq 25\%$ of defecations.
 - f) Fewer than 3 defecations per week.
2. Loose stool rarely present without use of laxatives.
3. Does not satisfy the diagnostic criteria for IBS.

Source: Rome III Diagnostic Criteria for Functional Gastrointestinal Disorders [4].

*At least 2 of the criteria fulfilled for the last 3 months with symptom onset at least 6 months prior to diagnosis.

The major symptom of CIC is a decrease in SBM frequency. SBM has been assessed in previous studies in CIC, and is typically calculated by stool frequency in a week (SBM denotes a bowel movement occurring without the use of a laxative, suppository, or enema within the preceding 24 hours) [6,7].

This phase 3, randomized, double-blind, placebo-controlled study is aimed at scientifically and objectively evaluating the efficacy and safety of lubiprostone in subjects with CIC. The study design allows for independent assessment of efficacy and safety in these subjects to support registration.

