7.3 Excluded Medications and Procedures

7.3.1 Excluded Medications

Subjects must be instructed not to take any medications including over-the-counter products, without first consulting with the investigator.

Due to the potential influence on the efficacy evaluation of lubiprostone, the following medications are to be excluded during the course of the study and must be discontinued no later than Day -15 of the Screening period through the Final Visit or Early Termination Visit:

- Anticholinergic drugs or drugs with anticholinergic effect (except ipratropium bromide or any inhaled or nasal-spray forms of this medication).
- Opioids.
- Antispasmodics.
- Cholinesterase inhibitors.

- Antidiarrheal medications.
- Anticonstipation medications (eg, linaclotide).
- Gastrointestinal prokinetic agents.
- Laxative agents (eg, PEG 3350), including homeopathic remedies.
- Tricyclic antidepressants.
- Any medications at the discretion of the investigator known to relieve or cause constipation or constipation symptoms.

The use of excluded medications listed above should be documented as concomitant medications. The Medical Monitor must be notified in advance (or as soon as possible thereafter) of any instances in which excluded medications are taken, or to be taken. Continued participation of the subject will be at the discretion of the Sponsor.

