7.8.1 Primary Efficacy Endpoint(s)

The primary efficacy endpoint is SBM frequency at Week 1; an SBM is defined as any BM that does not occur within 24 hours after rescue medication use. Since rescue medication use will be disallowed during Week 1, the SBM frequency should equal the BM frequency. In the case of protocol violators, the analysis will be based on SBMs.

In order to adjust for early withdrawals or those with less than 7 days diary data, weekly SBM frequency will be calculated as follows:

$$7 \times (\text{Number of SBMs} / \text{Number of days}),$$

where the number of days is the number of days during the week that the subject was in the study. Weeks will be calculated as 168-hour intervals starting from the day after randomization (Day1), if there is no time recorded for the morning dose on Day1 then the time of the first recorded morning dose will be used. The number of days will generally be 7 unless a subject drops out during a treatment week. If the number of days is less than 4, then the data will be considered insufficient and the frequency will be missing.

Primary Analysis

Since outliers are commonly observed in these data, parametric models may not be robust. The efficacy data will therefore be analyzed by a van Elteren test stratified by center. If necessary, small centers will be pooled as mentioned above. This procedure will test the null hypothesis of equal SBM rates between treatments at the end of Week 1 versus the alternative hypothesis of non-equality between the 2 groups; the test will be conducted at a 2-sided significance level of 0.05. A related 95% confidence interval and point estimate will be provided for the treatment difference; the confidence interval will be estimated by inverting the hypothesis test. This endpoint will be analyzed for the FAS.

Sensitivity Analyses

The primary analysis as described above will be repeated using the PP rather than the FAS. An additional sensitivity analysis using the FAS assuming a ‘worse-case’ scenario approach will also be conducted, where missing values, including those with < 4 days diary data, are assigned the worst case values (the lowest SBM frequency for week 1) recorded in the study by any subject for that endpoint at that time.

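### The protocol holds two SBM definitions, and the narrower one used for the primary endpoint counts bowel movements that follow a non-rescue laxative

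*SAP*

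**What the plan says.** Two definitions of a spontaneous bowel movement stand in the documents.

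- Protocol 6.2, in explaining the choice of endpoint: "SBM denotes a bowel movement occurring without the use of a laxative, suppository, or enema within the preceding 24 hours".
- Protocol 13.1.3.1 (Primary Endpoint) excludes only movements in the 24 hours after rescue medication. SAP 7.8 repeats it: "An SBM is defined as any BM that does not occur within 24 hours after rescue medication use". SAP 7.8.1 uses the same rule.

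The derivation follows the second: "Certain periods after taking rescue medication will be defined as “blackout periods” during which BMs are considered as non-spontaneous". Every blackout rule in SAP 7.8, including those for missing times, starts from rescue intake.

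For other laxatives, Protocol 7.3.1 lists among the excluded medications "Laxative agents (eg, PEG 3350), including homeopathic remedies". It has any use recorded as concomitant medication and adds: "Continued participation of the subject will be at the discretion of the Sponsor". Withdrawal is not automatic.

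Use of an excluded medication before the primary assessment removes a subject from the per-protocol set (Protocol 13.1.1, SAP 7.2). The primary analysis is on the FAS, which has no such exclusion, and SAP 7.8 calls the per-protocol analyses supportive.

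**The concern.** A prohibited laxative taken in Week 1 and entered only as concomitant medication starts no blackout. The movements it produces then count as spontaneous, although Protocol 6.2 would not count them.

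The SBM flag also feeds SBM frequency at Weeks 2 to 4, the proportion with an SBM within 24 hours of first dose, and the weekly means of straining and stool consistency, which are averaged over SBMs. SAP 7.8.1 says that for protocol violators the analysis rests on SBMs, so the SBM definition is meant to be the safeguard. It does not cover this kind of violator.

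If such use were commoner on placebo, placebo counts would rise and the difference would shrink.

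**Working it through.** **1. The plan's own figure.** Inputs (Protocol 13.3, SAP 6.0): means 4 and 5.9, SD 4, two-sided alpha 0.05, power 90%, Wilcoxon-Mann-Whitney test, total 198.

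- Normal formula per arm: 2 × [4 × (1.960 + 1.282) / 1.9]² = 93.14.
- Divided by the Wilcoxon relative efficiency 3/π: 97.54, so 98 per arm, 196 in total.
- The noncentral-t version gives 95 per arm, and 200 in total after the same division.

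These bracket 198, so the figure is reproduced. The SBM definition does not enter the formula, so the sample size is unaffected. With 99 per arm, power is 90.4% (normal formula with 3/π).

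**2. The two definitions applied to the same records.**

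- *Bisacodyl suppository or glycerin enema given as rescue:* not spontaneous under either.
- *Another agent chosen by the investigator when these fail:* Protocol 6.1 calls it another rescue medication, so not spontaneous under either when it is a laxative, suppository or enema.
- *Laxative taken by the subject and recorded only as concomitant medication:* not spontaneous under Protocol 6.2, but an SBM under Protocol 13.1.3.1 and the SAP.
- *PEG taken by the subject:* not spontaneous under Protocol 6.2, and unclear under the SAP. Protocol 6.1 says of PEG, linaclotide, methylnaltrexone and prucalopride "all of which are considered prohibited rescue medications". The SAP does not say whether a prohibited rescue medication starts a blackout, so two programmers could derive different counts.

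**3. Size, by assumption only.** The documents give no rate of non-rescue laxative use, no split by arm and no number of extra movements.

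- Shift = (placebo share − lubiprostone share) × extra movements per user.
- With 2% against 1% and 2 movements: 0.01 × 2 = 0.02 SBM/week. With 5% against 1%: 0.04 × 2 = 0.08. These are 1% and 4% of 1.9.
- Standard error of the difference: 4 × √(2/99) = 0.57. The shifts are about 4% and 14% of it.

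With use on placebo only and SD held at 4:

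| Share of placebo | Extra movements | Difference | Power |
|---|---|---|---|
| none | – | 1.90 | 90.4% |
| 1% | 1 | 1.89 | 90.1% |
| 2% | 2 | 1.86 | 89.2% |
| 5% | 2 | 1.80 | 87.2% |
| 10% | 3 | 1.60 | 78.5% |

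Equal shares with equal extra movements in both arms give a shift of zero.

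**4. Baseline.** Laxatives stop at Visit 1 (Day -15), and SAP 7.8 takes baseline from Days -14 to -1. The 24 hours after a Day -15 dose reach only part of Day -14, one day of 14 and before randomisation. Baseline is not in the van Elteren test. It enters the primary analysis only as the imputed value where no post-baseline data exist.

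**The case against.** A reader might infer that the SAP departs from the protocol. It does not: it matches Protocol 13.1.3.1, the section attached to the primary endpoint. The wider wording is a parenthesis in a sentence on how SBM was assessed in earlier constipation studies. The conflict lies inside the protocol.

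A reader might also infer that comparability with the earlier lubiprostone trials requires the wider wording, since Protocol 6.2 gives comparability as a reason for the endpoint. The documents do not state those trials' SBM definition, so this cannot be shown.

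The exposure is also narrow. Standard rescue agents and investigator-chosen substitutes already start a blackout. Laxatives are prohibited from Day -15. The diary asks daily about rescue use (SAP 7.7), and a subject who self-treats may answer yes there. The primary analysis is repeated on the per-protocol set, without users of excluded medication.

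All of this stands and limits the size. It does not close the gap. No section makes a movement after a non-rescue laxative non-spontaneous, the users stay in the FAS, and the per-protocol analysis discards the whole subject instead of correcting the count in the primary result.

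**Conclusion.** The inconsistency is real, and the operative rule gives a result that Protocol 6.2 would reject: some laxative-induced movements are counted as spontaneous in the FAS primary analysis and in the SBM-based secondary endpoints.

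The size cannot be derived from the documents and is probably small: 0.02 to 0.08 SBM/week under the assumed rates above. The mean difference is biased only if use, or its effect on counts, differs between arms. Excess use on placebo would pull it toward zero, so in that direction it would not create a false claim of efficacy.

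A claim of material bias in the primary result, or of a contaminated baseline, would go beyond what the documents support. This is a cheap improvement, not a threat to the trial's conclusion.

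**What to change.** Before unblinding:

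1. Use one SBM definition in Protocol 6.2, Protocol 13.1.3.1 and SAP 7.8 and 7.8.1.
2. Start the 24-hour blackout from any laxative, suppository or enema, whether recorded as rescue or as concomitant medication. Identify the agents from a pre-specified coded-medication list finalised at the blinded data review. This also settles how self-taken PEG is treated.
3. State the timing rule. Where a concomitant entry has a date but no hour, apply the existing 0-48 hour rule from midnight. For start-stop ranges, treat each recorded day of use as an intake.

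A related premise should be settled at the same time. SAP 7.8.1 says: "Since rescue medication use will be disallowed during Week 1, the SBM frequency should equal the BM frequency". Protocol 6.1 bars rescue only from 24 hours before to 48 hours after the first dose. The two passages must be reconciled.

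The cost is a few sentences and a medication list. Concomitant medications are already collected and WHODrug-coded (SAP 7.6). The downside is timing: the sample diary (Protocol Appendix E) asks date and time for rescue but gives neither for concomitant drugs. Some blackout windows will therefore be wider than 24 hours, and a long start-stop range could black out most of a week. Because the denominator remains days in the study, a wider window lowers that subject's SBM rate.
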